We will use the killed whole cell oral cholera vaccine, Shanchol™ as well as an oral placebo for the study. The vaccine is manufactured by Shantha Biotechnics, in Hyderabad, India and registered in India and is prequalified by the WHO. Shanchol™ is available in a single dose vial. The study agents will be supplied by the company and imported by approaching the Directorate General of Drug Administration of Bangladesh. Both the vaccine and placebo will be transported from the manufacturer to a designated EPI cold room at Mohakhali, Dhaka arranged for this study where it will be stored. We will identify vaccination centers within the intervention areas. These sites may include the government's EPI outposts, non-government facilities utilized during national immunization days, or other appropriate facilities which are easily accessible by the target population (Appendix 1C). Study agents will be maintained at 2-8°C. Immunization will be carried to the study population in three phases. Vaccination teams composed of the required number of vaccinators, record keepers, consent takers, supervisors, and other support staff will be present at each vaccination site (approximately 30 sites). Each participant over

the age of one year and non pregnant females living in communities will be individually randomized to receive vaccine or placebo.

Pregnancy status will be enquired verbally for all married women of child bearing age during the census update as well as before vaccination to exclude them from the study. If she is uncertain about her pregnancy status, she will be asked for her last menstrual period (LMP). All married females will be asked about their last LMP, if this is more than four weeks prior, irregular, or unknown, will be considered ineligible for the study. Pregnancy status in married women will also be ascertained at least two months after vaccination by home visits of trained field staff. Those who will be confirmed for pregnancy at this time point will be followed up at 6 months as well as with further visits monthly to ascertain pregnancy outcome after delivery. A pregnancy followup questionnaire will be used after consent taking for these visits (Appendix 6A, 6 B).

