The DSMB will also be responsible for un-blinding the randomization number codes in the event of severe putative vaccine reactions. Otherwise, the codes will not be revealed until the end of the trial and until the computerized dataset has been frozen. If the intervention assignment is un-blinded, all study collaborators will be notified immediately.

Measurements

Census update

The census in the study population will be updated every six months after intervention with the study agents. During this process in-migrants within the study area will get a SCVB card with unique ID to ease the disease surveillance process. Data collectors will visit each house in the intervention areas and collect information on births, deaths, migrations (in/out), missed in previous census, change in marital status, pregnancies and other events (Appendix 1D).

Disease Surveillance

1. Surveillance at the icddr,b hospitals in Mohakhali and Mirpur

All patients from the study area presenting for care at the hospital with diarrhea will be included in routine hospital surveillance. A diarrhoeal visit is defined as a visit by a patient who has in the 24 h before presentation, three or more loose or liquid stool or at least 1 bloody loose stool or any number of loose stools with signs of dehydration present, as stated in criteria used at the icddr,b hospitals[29]. The assessment of dehydration status in diarrhea will be carried out by trained personnel.

The diarrheal disease surveillance for the project will be conducted at icddr,b hospitals at Mohakhali and Mirpur and other health facilities for patients coming from the Mirpur study area (wards 7-13, 15 and 41). Clinical staff at each of the two hospitals and other facilities will evaluate each patient at the hospital triage area and provide treatment as per the routine procedure. Internal clinical monitoring for quality control will also be carried out for hospitalized study patients using a disease surveillance questionnaire (Appendix 2B). Around 5% of the study patients will be further evaluated immediately after admission. A trained physician will function as the safety monitor for the study and will oversee

clinical procedures for patient enrolment and management during surveillance to monitor GCP practice and trial conduct.

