Plasma vibriocidal antibodies to *V. cholerae* O1 (El Tor Inaba; strain T19479; El Tor Ogawa; strain X25049) will be evaluated by a microtiter assay. To measure vibriocidal antibodies to *V. cholerae* O139, the partly encapsulated vaccine strain CIRS 134 will be used [35]. The vibriocidal titre will be defined as the highest dilution causing 50% inhibition of bacterial growth. Two-fold serial dilutions of pre- and post-immunization specimens will be tested side-by-side in duplicates on each plate. Titres will be adjusted in relation to a reference serum specimen included in each test to compensate for variations between analyses on different occasions. The vibriocidal antibody titre ascribed to each sample will be the mean of the duplicated determinations, which will not be allowed to vary more than one two-fold dilution for either the reference or the test sera. The tests will be repeated if larger variations are observed. A four-fold or greater increase in titre between pre- and post-immunization specimens will be taken to represent seroconversion.

To control for variations, test plates will contain pooled convalescent serum sample from patients with cholera as a positive control (pooled O1 Ogawa, O1 Inaba and O139 sera from our collection of specimens from cholera patients) [32, 35, 36]. When progressing from one phase of the study to another, laboratory pooled control specimens will also be used [25]. This will validate the specificity of the assay further. An increase of vibriocidal antibody titer by 4-fold or higher between acute and convalescent sera will be considered a significant antibody response.

Active follow up for safety:

We will select 6,000 participants purposively from the study participants after verbal consent is obtained. These 6,000 participants will be actively followed once every two weeks for safety outcomes for a 28 day period after study agent administration. A questionnaire will be used for documenting and reporting solicited safety outcomes in this subset of the study population (Appendix 4A). Number of

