Neither the bivalent, killed, oral cholera vaccine nor the placebo is known to cause any significant adverse reactions. However, as a precaution, procedures will be in place to detect adverse events in the trial participants as follows: At the vaccination sessions after each dose, recipients will be requested to wait for half an hour at the site, where one staff member will be stationed to monitor any immediate adverse event following vaccination. Individuals with immediate adverse events will receive emergency treatment and the event will be recorded on the form. The adverse event or serious adverse event form will be reported using Medications, Adverse Events, and Serious Adverse Event forms (Appendix 4A, 4B, 4C) and will be reported within 28 days after vaccination whether they are considered vaccine-related or not.

Definition of Adverse event:

An adverse event will be defined as an untoward medical event (diarrhea, vomiting, abdominal pain/cramps or any other local and systemic symptoms) after receipt of a dose which may or may not be

associated with the vaccine. Adverse events will be monitored passively in all participants up to 28 days after vaccination.

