A serious adverse event (experience) is any untoward medical occurrence that results in death or is life-threatening. The term “life-threatening” in the definition of “serious” refers to an event in which the

recipients will be at risk of death at the time of the event; it does not refer to an event, which hypothetically might have caused death, if that were more severe.

A serious adverse event (SAE) is defined as an AE meeting one of the following conditions:

- Death during the period of protocol-defined surveillance
- Life-threatening event (defined as a study participant at immediate risk of death at the time of the event)
- An event requiring hospitalization or prolongation of existing hospitalization during the period of protocol-defined surveillance. In case of diarrhea, an SAE will be one that requires admission to an inpatient ward for >24 hours.
- Results in congenital anomaly or birth defect, or malignancy
- Results in a persistent or significant disability/incapacity

Any other important medical event that may not result in death or be life threatening, may be considered a serious adverse event when, based upon appropriate medical judgment, the event may jeopardize the study participant and may require medical or surgical intervention to prevent one of the outcomes listed above. Prudent medical judgment must be exercised to decide whether reporting is appropriate.

Reporting Procedures of Serious Adverse Events

All SAEs that occur during the study will be reported by study PI or designee within 24 hours to the ERC and the DSMB as well as to IVI and ShanthaBiotechnics. The SAE form will always be completed as thoroughly as possible with all available details of the event, signed by the principal investigator. If the investigator does not have all the information regarding an SAE, he/she will not wait to receive additional information before submitting the report. If deemed necessary, the DSMB will have the authority to call a temporary suspension of the study, for careful review and assessment of the reported event(s). The study physicians/medical officers will follow-up the participants with SAEs until the event has: resolved, subsided, stabilized or disappeared or the event is otherwise explained, or the participant is lost to follow-up. The date of final disappearance of the adverse event will be documented. The study physician will always provide an assessment of causality at the time of the initial report.

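### Pregnancy-outcome follow-up admits only women still pregnant at a visit two months or more after dosing, so earlier losses of exposed pregnancies are not systematically captured

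*Supplement*

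**What the plan says.** All references are to the latest protocol version unless the Data Analysis Plans are named.

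- **Screen before dosing (Delivery of study agent).** Pregnancy is asked about verbally, and all married women are asked for their LMP: "if this is more than four weeks prior, irregular, or unknown, will be considered ineligible for the study".
- **Visit after dosing (same section).** "Pregnancy status in married women will also be ascertained at least two months after vaccination by home visits of trained field staff". No latest date is set.
- **Entry to outcome follow-up (same section).** "Those who will be confirmed for pregnancy at this time point will be followed up at 6 months", with monthly visits after that until the outcome is known. A pregnancy questionnaire (Appendix 6A, 6B) is used at these visits. The appendix is not among the pages available.
- **General safety reporting (Definition of Adverse event).** "Adverse events will be monitored passively in all participants up to 28 days after vaccination".
- **Active subset (Active follow up for safety).** "These 6,000 participants will be actively followed once every two weeks for safety outcomes for a 28 day period after study agent administration".
- **Serious adverse events (Reporting Procedures of Serious Adverse Events).** "All SAEs that occur during the study will be reported by study PI or designee within 24 hours". The listed criteria do not name pregnancy loss.
- **Census update.** Six-monthly house visits collect, among other items, "change in marital status, pregnancies and other events". Losses are not named.

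The secondary safety endpoints do not mention pregnancy outcomes, and the Data Analysis Plans contain no pregnancy analysis.

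**The concern.** The protocol goes to some trouble over inadvertent exposure in pregnancy. It plans home visits, repeated follow-up, a questionnaire and verbal consent for the monitoring. Yet the group followed is defined by still being pregnant at a visit two months or more after dosing. A woman who was pregnant when dosed and lost the pregnancy before the visit does not fit that definition, so the outcome data are left-truncated over the interval closest to exposure.

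If early loss were the same in both arms, the cost would be missing information. If it differed, that difference would not be counted directly, and the pregnancies that are followed would be selected differently by arm. Either way, a summary of the followed pregnancies would say nothing about early loss.

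A lesser point comes from the same rule. A woman found pregnant at the visit may have conceived before or after dosing, and no rule is stated for separating the two. Unexposed pregnancies would then dilute the exposed group.

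**Working it through.** The plan gives no figure for pregnancy outcomes, so there is none to reproduce. The check is one of timing, followed by an illustrative count.

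**Inputs.** LMP at most 28 days before dosing (Delivery of study agent); visit at day 60 or later (same section, two months taken as 60 days); end of passive and active adverse event surveillance at day 28; 6,000 in the active subset; 204,438 to be vaccinated and 1% pregnant (Sample size calculation for primary analysis).

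**Step 1: gestation, counted from LMP.** Weeks = (days from LMP to dosing + days since dosing) / 7, with 0 to 28 days from LMP to dosing if the history is accurate.

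| Time | Calculation | Weeks from LMP |
|---|---|---|
| Dosing | 0/7 to 28/7 | 0 to 4 |
| Day 28, adverse event surveillance ends | 28/7 to 56/7 | 4 to 8 |
| Day 60, earliest visit | 60/7 to 88/7 | 8.6 to 12.6 |
| Day 90, a later visit (assumed) | 90/7 to 118/7 | 12.9 to 16.9 |

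**Step 2: the uncovered interval.** 60 − 28 = 32 days at least, and longer if the visit is later.

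**Step 3: what each other route would record.**

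- Passive reporting: a loss by day 28, if the woman reports it or seeks care.
- Active visits: a loss by day 28 in 6,000/204,438 = 2.9% of those dosed.
- Serious adverse event reporting: a loss at any time in the study, if it meets a criterion such as hospitalisation or is judged an important medical event.
- Census: a pregnancy known at a six-monthly round. One that began and ended between rounds need not appear.

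A loss after day 28 that is not serious is covered by none of these in the text.

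**Step 4: illustrative count.** Treat 1% as the steady-state proportion pregnant among those dosed, and take 9.2 months as the duration of a pregnancy (both assumptions).

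- Pregnant at any time: 204,438 × 0.01 = 2,044.
- Conceptions in four weeks: 2,044 / 9.2 × (28/30.4) = about 205.
- With LMP at most four weeks ago and conception about mid-cycle (assumption), only about the last two weeks of conceptions can be present at dosing: 205 / 2 = about 102.
- Lost before the visit, at an assumed 10% to 20%: 102 × 0.10 = about 10, to 102 × 0.20 = about 20, across both arms. That is about 5 to 10 per arm.
- Expected in the active subset, if it were representative: 102 × 0.029 = about 3 exposed pregnancies.

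**The case against.** **The routes in step 3 exist.** A reader might infer that these losses vanish from the safety data, or that every early loss is missed. The documents do not support that. Assessment of Safety also records events that a participant volunteers, so a loss need not reach a study facility to be recorded. What stands is narrower: capture is incidental, and none of these routes is designed for pregnancy loss.

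**The questionnaire is not shown.** It may ask about pregnancies that have already ended, so it cannot be said that such a woman could never be recorded. But the protocol ties the questionnaire to the follow-up visits, and the entry rule in the text turns on being pregnant at the two-month visit.

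**No comparison of pregnancy outcomes by arm is planned.** A reader might infer that the trial would report reassuring pregnancy outcomes that its design could not contradict. The objectives, safety endpoints and Data Analysis Plans propose no such conclusion. Under 1:1 allocation, a marked excess of early loss could also show as fewer followed pregnancies in one arm. These points limit the consequence; they do not fill the gap in the record.

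**Conception can be dated from data already planned.** This is largely right, since LMP is asked before dosing. Only the rule for using it is missing.

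**The documents do not rank early loss among possible effects of exposure.** That is correct, and the point does not need them to.

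**Conclusion.** The point holds in a limited form. Followed exactly, the plan leaves exposed pregnancies lost before about 8.6 to 12.6 weeks from LMP outside the dedicated follow-up, and later losses too if the visit is delayed. Some may surface through other routes, but a non-serious loss between day 28 and the visit has none specified.

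The size is illustrative: about 100 exposed pregnancies, with about 10 to 20 lost before the visit across both arms. It rests on accurate LMP histories, the 1% used as a steady-state rate (the protocol gives it only as an enumeration allowance), mid-cycle conception and the assumed loss rate. Counting a full four weeks of conceptions would double it, but does not fit the four-week LMP rule with mid-cycle conception.

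No efficacy endpoint or listed safety endpoint is affected. What is weakened is the completeness of the record on inadvertent exposure.

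**What to change.** In Delivery of study agent, state that the two-month home visit records any pregnancy since dosing, including those already ended, with LMP, end date and outcome. State that the LMP asked for at the screen will be used to classify conception as before or after dosing. If Appendix 6A/6B already contains these items, say so in the text and extend their use to this visit.

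Add a descriptive table to the Data Analysis Plans: exposed pregnancies and losses by arm, with pregnancies begun after dosing shown separately. With about 5 to 10 early losses expected per arm, no test should be planned and the table should not be presented as a powered comparison.

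The cost is a few questions at a visit already planned and one safety table. Some very early losses will be unrecognised or misdated; under blinding that error should be similar in the two arms.

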adverse events and serious adverse events in this subgroup who received 1 dose of vaccine or placebo and present for care of vaccine adverse effects at treatment settings or who die from the time of dosing until 28 days after dosing to be captured every 2 weeks active surveillance via solicited questionnaires. For this purpose, trained medical personnel will visit homes of participants every two weeks to collect medical history and assess the safety of the study agent.

Verbal Autopsy:

We will carry out 'Verbal Autopsy' in our study area where deaths will be identified through a household search by home visits which will be conducted by study staff. Verbal autopsy will be conducted on death cases identified by this procedure. The aim of the 'Verbal Autopsy' is to identify the number of deaths and the probable causes of death in this time period after receiving the investigational product. Consent will be obtained from a relative of the dead participant (Appendix 13A). We will use adopted WHO verbal autopsy questionnaire[44] to conduct verbal autopsy, (Appendix 13B). After identification, trained medical professional will visit homes of the deceased to perform verbal autopsy.

Sample Size Calculation and Outcome (Primary and Secondary) Variable(s)

Clearly mention your assumptions. List the power and precision desired. Describe the optimal conditions to attain the sample size. Justify the sample size that is deemed sufficient to achieve the specific aims.

Sample size calculation for primary analysis

In this placebo-controlled individually randomized trial, the primary analysis is to evaluate efficacy of the vaccine after six months following vaccination. Even this trial design is to test the conventional null hypothesis of no difference, a criterion that a confidence limit for relative risk is assumed less than a specified value for monitoring the outcome at six month. Therefore, we wish to show that the ratio of risk in population 1 (treatment group) to risk in population 2 (placebo group) is less than specific relative risk rather than 1. The usual null value of relative risk (R_0) is, therefore, required to be excluded by the pre-specified value, say 0.10; thus, the R_0 becomes 0.90 (1.00-0.10).

The sample size, N , for this study is, therefore, calculated based on logarithmic transformation method described elsewhere (Blackwelder, 1993) using the following formula

$$N = (z_\alpha + z_\beta)^2 [q_1/kp_1 + q_2/(1-k)p_2] / (\log R_0 - \log R)^2$$

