- Date of onset for first episode of watery diarrhea with severe dehydration detected in the study treatment centres from 7days to,6, 12,18and 24 months, respectively after dosing among those who received 1 dose of vaccine or placebo
- Date of onset for first episode of diarrhea with fecal excretion of *V. cholerae*O1 in non-participating subjects, who are detected within one of the study treatment centres from 7 daysup to 6,12,18and 24 monthsafter dosing of study participants.
- Date of onset for first episode of diarrhea with severe dehydration and fecal excretion of *V. cholerae*O1 in non-participating subjects, who are detected within one of the study treatment centres from 7 daysup to 6,12,18and 24 monthsafter dosing of study participants.

Secondary safety endpoints

- Number of adverse events and serious adverse events in participants who received 1 dose of vaccine or placebo and present for care of vaccine adverse effects at treatment settings or who die from the time of dosing until 28 days later (passive surveillance by type of complaint and by cause of death).

Secondary immunogenicity endpoints

- Geometric mean serum vibriocidal (to El Tor Inaba and Ogawa O1 serogroup organisms and to O139 serogroup organisms) titers measured in participants at baseline (day0) and 14 days after receipt of either vaccine or placebo.
- Four-fold or greater rises in titers of serum vibriocidal antibodies (to El Tor Inaba and Ogawa O1 serogroup organisms and to O139 serogroup organisms), relative to baselineday 0 and 14 two days after receipt of either vaccine or placebo

Analysis plan

To analyze vaccine protection, we will use Cox proportional hazard regression models verifying first that the proportionality assumption is satisfied for all independent variables. Checking of the proportional hazard assumption will be performed by plotting the observed standardized score with simulated realizations for each covariate in the model, and the p-value will be derived from the Kolmogorov-type supremum test based on 1,000 simulations. If a variable does not satisfy the proportionality assumption, then we will exclude the variable from the model. However, the critical variables such as vaccination status and age will be kept in the model irrespective of the results of the test for proportionality assumption.

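### The safety measure for the 6,000 actively followed participants counts only people who seek care or die, so solicited reactions found only at home visits belong to no defined endpoint

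*Supplement*

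**What the plan says.** All places are in the latest protocol unless stated.

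- **Specific Objectives, secondary.** The last objective is safety up to 28 days after the dose. It carries no condition about seeking care.
- **Active follow up for safety.** "These 6,000 participants will be actively followed once every two weeks for safety outcomes for a 28 day period after study agent administration". The purpose is given: "A questionnaire will be used for documenting and reporting solicited safety outcomes in this subset of the study population". The next sentence defines the count as adverse events and SAEs "in this subgroup who received 1 dose of vaccine or placebo and present for care of vaccine adverse effects at treatment settings", or who die by day 28. It ends by saying that these are "to be captured every 2 weeks active surveillance via solicited questionnaires". Medical personnel are then to visit homes.
- **Secondary safety endpoints.** One endpoint is listed: the number of adverse events and SAEs "in participants who received 1 dose of vaccine or placebo and present for care of vaccine adverse effects at treatment settings or who die" within 28 days. It is labelled as passive surveillance.
- **Assessment of Safety.** All events observed actively or volunteered are recorded, with severity and possible relation.
- **Safety Assessment, Monitoring and Reporting.** After dosing, recipients wait half an hour while "one staff member will be stationed to monitor any immediate adverse event following vaccination"; immediate events are treated and recorded. Adverse events "will be reported within 28 days after vaccination whether they are considered vaccine-related or not". Active surveillance in the 6,000 covers solicited AEs and all SAEs.
- **Data analysis plan.** The sections shown deal with efficacy only.

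**The concern.** Home visits with a solicited questionnaire exist to find reactions that do not bring people to a clinic. The severity table starts at Grade 1, which for headache, fatigue and myalgia means no interference with activity. Such events are unlikely to lead to a visit to a treatment setting.

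If the subset count is limited to people who sought care or died, the 28-day safety objective is answered by care-seeking even where better data exist. The direction of the error is towards too few reactions, in a vaccine given to healthy people from one year of age. The wording also leaves an analyst two defensible counts from the same forms, one from the collection rules and one from the stated measure. Prespecification should remove that choice before the codes are opened.

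**Working it through.** The protocol states no safety sample size, power or reaction rate, so there is no figure of its own to reproduce. The check is mainly a comparison of text.

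**1. What is collected against what is counted**

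| Source | Collected or recorded? | Covered by a stated endpoint or measure? |
|---|---|---|
| Facility presentation, or death, all dosed participants | Yes | Yes: Secondary safety endpoints, passive |
| Solicited reaction at a home visit, care also sought | Yes | Yes, through the care-seeking clause |
| Solicited reaction at a home visit, no care sought | Yes: Active follow up for safety; Assessment of Safety; Safety Assessment, Monitoring and Reporting | No |
| Immediate event in the half-hour wait | Yes, on the form | Unclear: depends on whether a vaccination site is a treatment setting, a term not defined for safety |

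**2. The contradiction inside one sentence.** The subset sentence opens with the care-seeking-or-death condition and closes with active solicited capture. Capture by questionnaire at home needs no care-seeking; the count requires it. The opening is almost word for word the passive endpoint, which suggests that it was carried over.

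**3. Whether another section fills the gap.** The endpoint list names only the passive endpoint. The promise to report solicited outcomes in the subset gives no measure: no proportion, grade, time window for analysis or comparison by arm. The shown sections of the data analysis plan contain no safety analysis.

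**4. Illustrative size.** Assumptions, none taken from the documents except the 6,000:
- 6,000 / 2 = 3,000 per arm, as 1:1 allocation would give on average;
- 5% with any solicited reaction;
- 2% to 10% of those seeking care;
- two-sided 0.05 and 80% power, so the multiplier is 1.96 + 0.84 = 2.80.

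Expected events per arm: 3,000 × 5% = 150 with any reaction. Care-seekers: 150 × 2% = 3 (0.1% of 3,000) to 150 × 10% = 15 (0.5% of 3,000).

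The smallest detectable comparison rate p2 for a baseline p1 solves, with each arm's own variance,

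p2 − p1 = 2.80 × sqrt{[p1(1 − p1) + p2(1 − p2)] / 3,000}

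| Baseline p1 | Events per arm at baseline | Solution p2 | Right-hand side | Ratio p2/p1 |
|---|---|---|---|---|
| 5% | 150 | 6.70% | 2.80 × sqrt[(0.0475 + 0.0625)/3,000] = 1.70 points | 1.3 |
| 0.5% | 15 | 1.15% | 2.80 × sqrt[(0.004975 + 0.01141)/3,000] = 0.65 points | 2.3 |
| 0.1% | 3 | 0.49% | 2.80 × sqrt[(0.000999 + 0.00490)/3,000] = 0.39 points | 4.9 |

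Using the baseline variance for both arms gives smaller ratios (1.3, 2.0 and 3.3). At low rates that understates the loss, because the higher rate also has the larger variance. With about 3 events per arm the normal approximation is rough, so the last row shows order of magnitude only.

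**The case against.** The strongest reply is that nothing is lost. The forms capture home-visit reactions, several sections require them to be recorded and graded, and the section on active follow-up promises to report solicited outcomes. On that reading the care-seeking clause is a pasting slip that nobody would apply. Much of this stands: the fault lies in the endpoint definition, not in data collection, and exclusion was probably not intended. What remains is that the only sentence naming a measure for the subset restricts it, and no other text supplies one.

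A reader might infer more than the documents support in four places.

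- **That the listed endpoint is itself wrong.** It is not. It is marked as passive surveillance for all dosed participants, and passive detection in at least 204,438 people has to depend on presentation.
- **That events must be judged vaccine-related to count.** The endpoint's phrase about vaccine adverse effects invites this, but an adverse event is defined as one that may or may not be associated with the vaccine. Assessment of Causality says that relatedness does not decide what is reported.
- **That everything seen in the half-hour wait is excluded.** Immediate events receive treatment, participants are told they may contact vaccination sites, and the window starts at dosing. A treated reaction may therefore count. An untreated one has no clear place.
- **That the active follow-up adds nothing, or that a real difference would be reported as none.** The commitment to report solicited outcomes stands against both.

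**Conclusion.** The point holds as an internal contradiction with a missing endpoint. The protocol gathers solicited reactions in 6,000 people but defines the subset's measure by care-seeking or death, and lists no endpoint for the active subset. Taken literally, it would under-count mild and moderate reactions against an objective that has no such limit.

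The textual conclusion rests on no assumed rate. The size does: a move from a detectable increase of about 1.3-fold to between about 2.3-fold and 4.9-fold depends on the assumed 5% reaction rate, 2% to 10% care-seeking and 3,000 per arm. The matter should be corrected because it affects a stated secondary objective. It does not touch the primary efficacy analysis or the SAE reporting procedures.

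**What to change.** 1. In Active follow up for safety, delete the clause about presenting for care from the measure for the 6,000.
2. In Secondary safety endpoints, add an active-subset endpoint: the proportion of the 6,000 with each solicited symptom by maximum grade, and the proportion with any SAE, to day 28, by arm, whether or not care was sought and regardless of judged relation.
3. Keep the passive endpoint for all dosed participants, but replace the words vaccine adverse effects with adverse events, to agree with the adverse event definition and Assessment of Causality.
4. State that immediate events recorded during the half-hour wait are counted.

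The cost is protocol wording and one further safety table. No new visits or forms are needed, since the data are already recorded and graded. Reported adverse event rates will be higher than under the literal wording, and the report should say why.
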